There was no evidence of drug related carcinogenicity in mice or rats. Mice and rats received lacosamide once daily by oral administration for 104 weeks at doses producing plasma exposures (AUC) up to approximately 1 and 3 times, respectively, the plasma AUC in humans at the maximum recommended human dose (MRHD) of 400 mg/day. Lacosamide was negative in an *in vitro* Ames test and an *in vivo* mouse micronucleus assay. Lacosamide induced a positive response in the *in vitro* mouse lymphoma assay. No adverse effects on male or female fertility or reproduction were observed in rats at doses producing plasma exposures (AUC) up to approximately 2 times the plasma AUC in humans at the MRHD.

3.12 **Human Toxicity:**

Likely (occurring in more than 20% of patients)

- Dizziness

Common (occurring in 3 – 20% of Patients)

- Vertigo
- Diplopia
- Blurred vision
- Nausea
- Vomiting
- Diarrhea
- Fatigue
- Headache
- Ataxia
- Somnolence
- Tremor
- Nystagmus
- Imbalance (possibly with associated falls)

Rare but Serious (occurring in fewer than 3% of patients)

- Suicidal ideation or behavior
- PR prolongation, first degree AV heart block
- Atrial fibrillation or flutter
- Syncope
- Multi-organ hypersensitivity reactions (also known as Drug Reaction with Eosinophilia and Systemic Symptoms, or DRESS)

3.13 Clinical Pharmacokinetic Properties:

The pharmacokinetics of lacosamide has been studied in healthy adult subjects (age range 18 to 87), adults with partial-onset seizures, adults with diabetic neuropathy, and subjects with renal and hepatic impairment. Lacosamide is completely absorbed after oral administration with negligible first-pass effect with a high absolute bioavailability of approximately 100%. The maximum lacosamide plasma concentrations occur approximately 1 to 4 hours post-dose after oral dosing, and elimination half-life is approximately 13 hours. Steady state plasma concentrations are achieved after 3 days of twice daily repeated administration. Pharmacokinetics of lacosamide are dose proportional (100-800 mg) and time invariant, with low inter- and intra-subject variability. Compared to lacosamide, the major metabolite, O-desmethyl metabolite, has a longer T_{max} (0.5 to 12 hours) and elimination half-life (15-23 hours).

3.14 Administration: Oral.

3.15 Supplier:

Lacosamide is commercially available, but study drug and identical placebo will be supplied by UCB.

3.15.1 Agent Distribution:

Ordering Study Agent/s:

See Section 15.3.2

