11.0 STATISTICAL CONSIDERATIONS

11.1 Overview

The primary analysis for this study is a randomized, two-arm, parallel group, multicenter trial enrolling post-operative patients with newly-diagnosed high-grade glioma (HGG). Patients will be randomly assigned to either lacosamide (L) or placebo (P). Patients will be randomized to either treatment using a 1:1 randomization scheme. Based on a retrospective review of available data we assume a 20% seizure risk in the P group and 8% in the L group (after 1 year of observation). Based on these assumptions and assuming that time to first seizure follows an exponential distribution we estimate the hazard ratio between the L and P arms to be 0.374. Additional assumptions of the trial are that patients will be administratively censored after 1 year of follow-up and that 15% of patients will be lost to follow-up. The reason for the first assumption is that risk of seizure is greatest during the first year and as such clinical interest focuses on this time period. Because standard software packages do not incorporate administrative censoring we developed a SAS IML program to estimate the power associated with this clinical trial design.

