Based on this simulation program, the maximum fixed sample size to be accrued is 298 patients. The power for this analysis is 83.6% (power based on 1000 simulations). Because we plan 1 interim analysis using an O'Brien-Fleming stopping rule, we will need to adjust the sample size upward using the group sequential-to-fixed sample size ratio of 1.008 [35]. While this ratio is exact for trials with 80% power, it is a conservative lower bound for trials with greater than 80% power [35]. This ratio results in a trial with 302 patients (i.e., the largest even integer greater than 298×1.008). This results in a trial with 151 patients randomized to L and 151 patients randomized to P. The primary measure of efficacy is time to first seizure (TFS). The primary test of the difference in TFS between the treatment arms will be based on the likelihood ratio statistic for the treatment effect in a stratified proportional hazards regression model with anticonvulsant use as the stratification factor. The MDACC DSMB will periodically meet (either once every 6 months or annually) to evaluate safety and efficacy. The interim analysis will take place after 21 events have been observed. We will assess efficacy using an O'Brien-Fleming stopping rule with a nominal critical value of 2.7959 at the interim analysis. A futility analysis based on a conditional power assessment may be performed if the hazard ratio between the two treatment arms is approximately 1. If a conditional power assessment is performed and the conditional power is less than 0.10 the trial will be stopped for futility. The decision to perform this futility analysis will include an assessment of the number of events observed (i.e., at least 50% of the expected 42 events have occurred and all patients have not yet enrolled in the trial). If the study continues to full accrual, the final analysis will take place when all of the patients have either been followed for 1 year or have experienced a seizure event. We will test the null hypothesis $HR=1.00$ against $HR \neq 1.00$ at the 0.05 level. The conditional power for the time-to-event outcome will be computed based on the method described in Design and Analysis of Clinical Trials with Time-to-Event Endpoints (Peace 2009, page 60) and Lan Simon and Halperin (1982).

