Descriptive and inferential statistics will be used to summarize the treatment effects. The mean, standard deviation, median, 25% percentile, 75% percentile, minimum, and maximum will be reported for continuous variables by treatment group. For discrete (qualitative) outcomes, descriptive analyses will be based on the distribution of these discrete outcomes and will be reported as percentages and patient counts by treatment. Time to event endpoints will be descriptively summarized by Kaplan-Meier curves. Point and interval estimates of treatment effects will be based on maximum likelihood methods. For binomially distributed variables, we will report proportions, their 95% confidence intervals, differences in proportions and 95%

confidence intervals for the difference in proportions. Estimates of treatment effects for time to event endpoints will be based on the ratio of hazard functions (L: P) using Wald type scores from a Cox proportional hazards regression model. Unless stated otherwise, all statistical tests will be assessed using a two-sided $\alpha = 0.05$ significance level and confidence intervals will be constructed using two-sided 95% and will be based on the normal approximation. Although multiple secondary endpoints will be evaluated we will make no adjustment for multiplicities associated with these multiple tests.

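### The default normal-approximation interval under-covers single low proportions, mainly because its upper limit is too low; changing the default is a cheap reporting improvement

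*Combined protocol and SAP*

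**What the plan says.** Section 11.1 commits to interval estimates for binary outcomes: "For binomially distributed variables, we will report proportions, their 95% confidence intervals, differences in proportions and 95" (the sentence continues to percent confidence intervals for the difference). It adds that "Point and interval estimates of treatment effects will be based on maximum likelihood methods". The method is then set for the whole plan: "confidence intervals will be constructed using two-sided 95% and will be based on the normal approximation". That sentence allows for exceptions stated elsewhere, so it is a default. I found no exception for low rates or small counts.

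Low rates are expected in two places. For seizures, Section 11.1 says "we assume a 20% seizure risk in the P group and 8% in the L group (after 1 year of observation"), and Section 1.3 makes the one-year risk of first seizure a secondary objective. For safety, Section 3.12 has a class headed "Rare but Serious (occurring in fewer than 3% of patients"), which includes suicidality, PR prolongation, atrial fibrillation or flutter, and syncope. Section 2.5 reports ALT elevations in 7/935 (0.7%) of lacosamide patients in earlier trials. Section 11.2.5, on adverse events, plans summaries and listings and names no interval method.

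**The concern.** With maximum likelihood estimates, the normal approximation for a proportion is ordinarily the Wald interval. Its half-width is computed from the observed proportion. A low count by chance therefore gives both a low estimate and a short interval, and the upper limit can fall below the true risk. At zero events the width is zero. At one, two or three events out of 151 the lower limit is negative.

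What is at stake is the printed upper bound on a risk. In a prophylaxis trial in patients without recent seizures, a reader will want to know how high a rare toxicity rate, or the residual seizure risk on lacosamide, could plausibly be. An interval labelled 95% that is too short on that side understates it.

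**Working it through.** **Inputs.** 151 patients per arm, one-year risks of 20% and 8%, and 15% loss to follow-up (Section 11.1). 151 × 0.85 = 128, so 120 to 151 is a reasonable range of arm sizes. Rare-event rates of 1% and 2% lie within the under-3% class of Section 3.12. They are illustrations, because the plan gives no expected rates for this trial.

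**The plan's own figures.** The plan states only the nominal 95%, so there is no achieved coverage to reproduce. Its risks do reproduce its effect size: ln(0.92)/ln(0.80) = 0.3737, against "we estimate the hazard ratio between the L and P arms to be 0.374". So 8% and 20% are used as one-year cumulative risks.

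**Formulas** (z = 1.96, x events, p̂ = x/n).
- Wald: p̂ ± z√[p̂(1−p̂)/n].
- Wilson: {p̂ + z²/2n ± z√[p̂(1−p̂)/n + z²/4n²]} / (1 + z²/n).
- Exact coverage at true p: the sum of Binomial(x; n, p) over all x whose interval contains p.

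**Worked cases, n = 151.**
- True 8%: the Wald interval contains 8% when x is 8 to 20. The upper limit is too low (x ≤ 7) with probability 7.7%, and the lower limit too high (x ≥ 21) with probability 0.9%. Coverage is 91.3%. Wilson contains 8% when x is 6 to 18, and covers 95.1%.
- True 2%: at x = 1 the Wald upper limit is 1.96%, just below 2%. That near miss pulls coverage down to 80.3%.
- True 1%: Wald misses whenever x = 0, which has probability 0.99^151 = 21.9%. Coverage is 78.0%.

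**Single proportions.** Exact coverage jumps with n and p, so the mean over n = 120 to 151 is shown beside the n = 151 value.

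| True rate | Wald, n = 151 | Wald, mean | Wilson, n = 151 | Wilson, mean |
|---|---|---|---|---|
| 20% | 94.5% | 94.3% | 94.7% | 95.0% |
| 8% | 91.3% | 93.1% | 95.1% | 95.2% |
| 2% | 80.3% | 91.3% | 96.7% | 96.1% |
| 1% | 78.0% | 74.2% | 93.4% | 95.2% |

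**Printed intervals.**
- 0/151: Wald 0 to 0; Wilson 0 to 2.5%.
- 1/151: Wald −0.6% to 2.0%; Wilson 0.1% to 3.7%.
- 12/151: Wald 3.6% to 12.3%; Wilson 4.6% to 13.4%.

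**Differences, 151 per arm, exact joint enumeration.**

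| True rates | Wald coverage | Newcombe coverage | Mean width, Wald to Newcombe |
|---|---|---|---|
| 20% v 8% | 94.9% | 95.3% | 0.153 to 0.156 |
| 3% v 1% | 92.4% | 97.0% | 0.0614 to 0.0774 (+26%) |
| 3% v 3% | 95.6% | 96.3% | 0.0757 to 0.0883 (+17%) |
| 1% v 1% | 97.0% | 99.1% | 0.0422 to 0.0651 (+54%) |

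For 30/151 placebo against 12/151 lacosamide, the difference (lacosamide minus placebo) is −19.6 to −4.2 points by Wald and −19.7 to −4.1 by Newcombe. These are the same for any practical purpose.

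**Kaplan-Meier one-year risk.** I simulated 20,000 trials with n = 151, 8% one-year risk, exponential event times and an assumed exponential 15% loss. The plain normal interval covers 93.1%, with the upper limit too low in 6.0% and the lower limit too high in 0.9%. The complementary log-log interval covers 95.8% (1.0% and 3.2%).

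**The case against.** The strongest reply is that nothing decisive depends on these intervals. The primary test is a likelihood ratio test in a stratified proportional hazards model, and no stopping or success rule uses a binomial interval. This stands, and it sets the weight of the point.

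The adverse-event part can also be challenged. Section 11.2.5 plans no intervals, and Section 11.1 describes discrete outcomes by counts and percentages, so a reader would see 0/151 directly. This stands in part. Intervals on adverse-event rates follow only from the general sentence on binomial variables, but if they are printed, the default governs them.

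Single coverage values can mislead. The 80.3% at 2% is near the bottom of an oscillation: at n = 128 coverage is 92.0%. At 8%, n = 128 gives 93.5%. The means are the fairer summary, and they still fall short.

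A reader might infer that the planned seizure-risk difference is also too short. The documents' own rates do not support that: coverage at 20% versus 8% is 94.9%. For sparse differences the Wald error goes both ways, under at 3% versus 1% and over at 1% versus 1%. Nor is Newcombe free there. It is conservative, and 17% to 54% wider in the sparse cases tabulated.

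Finally, Wilson does not settle the one-year seizure risk, which is censored by loss to follow-up. This stands: for that endpoint the complementary log-log interval is the relevant change.

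**Conclusion.** The point holds as a cheap improvement to reporting. For single proportions at low rates, the default interval covers less than its label says, and most misses come from an upper limit that is too low. On average over plausible arm sizes the shortfall is about 2 points at 8%, about 4 points at 2% and about 21 points at 1%. The 20% placebo proportion is close to nominal.

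A reader might take this to weaken the primary result or the planned efficacy contrast. It does neither: the primary test, sample size and power do not use these intervals, and the planned difference in proportions is covered at 94.9%.

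The verdict rests on three assumptions: that the normal approximation means the Wald interval; that rare-event rates resemble those quoted from earlier lacosamide experience; and that 120 to 151 patients per arm contribute. The Kaplan-Meier figures also assume exponential event times and exponential loss.

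**What to change.** Amend the default in Section 11.1 along these lines: intervals are two-sided 95%; single binomial proportions, including any adverse-event rate reported with an interval, use the Wilson score method; the one-year risk of first seizure is estimated by Kaplan-Meier, with an interval on the complementary log-log scale. The last is undefined only if an arm has no seizures, so add a fallback for that case.

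Newcombe intervals for differences in proportions are optional. They change nothing of note at the planning rates and matter only when events are sparse.

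The change costs a sentence or two and no patients or alpha. The real cost is width for rare events: at 1/151 the interval grows from 2.6 points (−0.63% to 1.96%) to 3.5 points (0.12% to 3.66%). Making the change before unblinding avoids an ad hoc choice if a 0-to-0 interval appears in the tables.

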11.2 Method of Analysis

11.2.1 Analysis Population

Intent-to-Treat (ITT) Population

This analysis set will include all subjects who (1) have received at least one dose of study medication; and (2) have no major protocol eligibility violations. Subjects with major eligibility violations that are identifiable based on pre-study entry characteristics will be excluded. Subjects who receive study medication other than that intended will be analyzed according to the therapy they intended to receive. No data collected on or after the first dosing date will be excluded.

Per-Protocol (PP) Population

All evaluable patients who do not experience any major protocol deviation will be included in the per-protocol dataset. This analysis set will include all subjects who (1) have received at least one dose of study medication; (2) have not committed any major protocol violation, and (3) are evaluable for primary endpoint. Subjects who received a treatment regimen other than that intended will be analyzed according to the therapy they received. Data collected after 30 days post permanent discontinuation of the study treatment will be excluded.

Safety Population

The analysis set will include all subjects who have received at least one dose of study medication. Subjects who receive study medication other than that intended will be analyzed according to the study medication received. All data collected up to 30 days after the subject permanently discontinues the study drug will be included in the analysis of this analysis set.

11.2.2 Baseline Characteristics

Demographic and baseline characteristics collected at screening or enrollment will be descriptively summarized on ITT and PP populations using:

- Frequency distributions (n, %) for qualitative outcomes,
- Standard statistical summaries for quantitative outcomes (n, mean, standard deviation, median, 25th percentile, 75th percentile, min, max).
- Both frequency distributions and standard statistical summaries will be reported for ordinal outcomes.

11.2.3 Safety Analysis

All safety analysis will be performed on the safety population.

11.2.4 Extent of Exposure

Duration of exposure to study drug will be expressed as the number of weeks between the first and last dose of study regimen, inclusive, regardless of temporary interruptions and dose reduction in study drug administration and summarized. Number of treatment cycles will also be summarized.

Dosing information for individual subjects will be listed and reasons for study drug discontinuations will be summarized.

11.2.5 Adverse Events

Clinical and laboratory adverse events will be coded using the NCI's Common Terminology Criteria for Adverse Events (CTCAEv4.0). The CTCAEv4.0 will be attached to the clinical database.

Summaries of unique adverse events will include

- all treatment emergent adverse events,
- all treatment emergent adverse events by the worst grade,
- all related treatment emergent adverse events,
- all related treatment emergent adverse events by the worst grade,
- all adverse events leading to study drug discontinuation

Treatment emergent adverse events are

- Events with onset dates on or after the start of treatment and up to 30 days after the permanent discontinuation of the study medication
- Continuing adverse events diagnosed before the start of treatment and getting worse in grade or relationship to treatment after the start of treatment.

Related adverse events include all those classified by the investigator as definitely, probably, or possibly related to the study drugs. Events for which the investigator did not record relationship to study drug will be considered related to study drug.

Multiple events will be counted once only per patient in each summary. In the presentation, Adverse Event Categories will be sorted in alphabetical order. Within Categories adverse events will be sorted in descending order of total events. For summaries by severity, the most severe event will be selected.

Deaths and serious adverse events

Serious adverse events and deaths will be listed. Data from the adverse event page that specify the event is serious will be used to generate the listing.

Summaries of serious unique adverse events will include:

- all serious treatment emergent adverse events,
- all related serious treatment emergent adverse events by the worst grade,

11.3 Patient Reported Outcomes.

The sample size for this trial was based on the primary endpoint of the study.

Received MDASI-BT forms will be checked versus the timing schedule and considered as valid if they fall within 14 days of the scheduled assessment. Compliance rates will be calculated as the number of received valid forms over the number of expected forms. Differences between groups in compliance will be tested by use of Fisher's exact test at every time point. We will use descriptive statistics to describe how patients rate symptom severity and interference with function at each time point. Error bar graphs for each of the symptoms will be constructed at each time point. The proportion of patients rating their symptoms to be 7 or greater (on a 0-10 scale) will also be reported. Differences of at least 2 points will be classified as the minimum clinically meaningful change in the symptom severity and symptom interference measures. For example, an increase of 2 points or more would mean a moderate improvement, whereas a decrease of 2 points or more would be interpreted as moderate worsening. For individual symptoms, a rise in a symptom score means deterioration, whereas a reduced score means improvement of the specific symptom.

Our primary analytic strategy involves the use of a random-effects (or latent growth curve) model to evaluate patient individual and overall longitudinal changes in symptom measures, and determine the impact of the use of AEDs on these parameters. The random-effects model approach provides a generalization to the classic linear regression model. It is ideally suited for analysis of repeated measures data in that it allows for more specific estimation of the correlation structure of the residuals, and more efficiently handles unbalanced designs and is very robust to missing data, without excluding participants or imputing values. In the model, we will include measure time, treatment indicator and their interaction as random effects (i.e., random slopes or latent growth curves). Such a model allows us to evaluate both patient individual and overall longitudinal trajectories of the symptom burden, and also determine the heterogeneity among patient's trajectories (i.e., variance of the random effects). Fit statistics, such as Akaike's Information Criterion (AIC) will be used to select appropriate covariance structure of the dataset. We will use a computer program, PROC MIXED (SAS v9.1 SAS Institute Inc, Cary, NC) to estimate and to test the models with continuous dependent measures. For binary symptom measures, we will use SAS PROC GLMIMX, which provides an adaptation to the mixed model approach for categorical data. To further investigate whether the patient population is consisted of several subpopulations characterized by different longitudinal trajectories. We will also conduct a latent class analysis based on the random-effects model. We allow different latent classes (or subpopulations) have different regression coefficients (i.e., different shapes of growth curves). The AIC will be used to determine the number of latent class and the maximum likelihood method will be used to estimate the unknown model parameters.

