2.0 BACKGROUND

2.1 High-grade gliomas and seizures

High-grade gliomas (HGG) are the most common type of primary brain tumor. There are approximately 22,000 new cases in the United States each year [1]. Seizures are the presenting symptom in approximately 20% of patients with supratentorial HGG and are present at some stage of the illness in 30-50% of patients [2, 3]. The standard of care for HGG patients who present with seizures includes the administration of antiepileptic drugs (AEDs) [4]. Likewise, there is general agreement that AED therapy is not indicated for patients with infratentorial or brainstem tumors due to the extremely low seizure risk. There is, however, no consensus regarding the administration of prophylactic AEDs to patients with supratentorial HGG who have not had seizures. In a 1996 survey of practice patterns according to subspecialty, 33% of radiation oncologists, 50% of oncologists, 53% of neurologists, and 81% of neurosurgeons reported administering prophylactic AEDs. The overall rate of prophylactic AED administration by the 115 physicians in the study was 55% [5]. A 2004 survey of the practice patterns of neurosurgeons in the United States found similar results. Of the 367 respondents, 285 (77.7%) reported the routine use of prophylactic AEDs in patients with HGG [6]. Finally, a retrospective study showed that 27% of 164 brain tumor patients treated in Canada between 2003 and 2005 received phenytoin despite no history of seizures [4].

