6.1.2 Supportive Care

- a. Dexamethasone should be used in the smallest dose to control symptoms of cerebral edema and mass effect, and discontinued if possible. Prednisone is not permitted because it induces CYP2C19.
- b. Febrile neutropenia may be managed according to the local institution's Infectious Disease guidelines. Measures may include appropriate laboratory testing, including blood and urine cultures and the institution of broad-spectrum antibiotics. If a source for the fever is not identified or the fever resolves when the neutrophil count recovers, antibiotics may be discontinued and the patient observed.
- c. The use of antiemetics will be left to the investigators' discretion.

d. Other Concomitant Medications

Therapies considered necessary for the wellbeing of the patient may be given at the discretion of the investigator. Other concomitant medications should be avoided except for analgesics, chronic treatments for concomitant medical conditions, or agents required for life-threatening medical problems. No other anti-convulsant medication are allowed while on the study. All concomitant medications must be recorded.

f. Surgery

If neurosurgical management is required for any reason, the procedure must be documented, including the indications for surgery, the surgical operative note and pathology report.

6.1.3 Definition of dose limiting toxicities (DLT):

Toxicities will be graded according to the NCI Common Terminology Criteria for Adverse Events (CTCAE) version 4.0. If multiple toxicities are seen, the presence of DLT should be based on the most severe toxicity experienced. DLT will be defined as any grade 3 toxicity that:

- Is not amenable to maximal medical management, and
- Is attributable to the study drug, and
- Occurs during treatment with lacosamide or placebo.

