10.0 CRITERIA FOR REMOVAL FROM TREATMENT

10.1 Criteria for Removal from Protocol Treatment:

- a. Completion of one year of therapy.
- b. Unacceptable toxicity (**see Section 6.1.3**).
- c. Seizure (as defined in Section 9.1).
- d. The patient may voluntarily withdraw from treatment at any time for any reason.
- e. Medical or psychiatric illness which in the investigator's judgment renders the patient incapable of further therapy.
- f. Pregnancy.

All reasons for discontinuation of treatment must be documented in the flow sheets.

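### The 30-day treatment-emergent window takes in side effects of a non-study antiepileptic drug started after a seizure, and if lacosamide works more placebo than lacosamide patients enter the window that way

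*Combined protocol and SAP*

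**What the plan says.** - Section 11.2.5 defines treatment-emergent events as "Events with onset dates on or after the start of treatment and up to 30 days after the permanent discontinuation of the study medication". It also includes earlier events that worsen after treatment starts.
- Section 11.2.1 sets the same limit for the Safety Population: "All data collected up to 30 days after the subject permanently discontinues the study drug will be included".
- Section 10.1 lists among the reasons for removal from treatment "Seizure (as defined in Section 9.1".
- Section 2.1 states: "The standard of care for HGG patients who present with seizures includes the administration of antiepileptic drugs (AEDs". No section prescribes what follows a seizure on study.
- Section 6.1.2(d) says "No other anti-convulsant medication are allowed while on the study". It does not say whether this still applies once study drug has been stopped for a seizure.
- Section 11.1 gives the design rates: "we assume a 20% seizure risk in the P group and 8% in the L group".
- Figure 8-1, footnote a, schedules the four-weekly adverse event calls for the time on treatment. Section 15.12, step 10, requires 30 days of follow-up for unblinded patients who had a serious adverse event.

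**The concern.** The 30-day rule is worded identically for both arms, but the event that most often separates the arms, a first seizure, is also the primary endpoint. A seizure stops study drug and opens a 30-day off-drug period that still counts towards the randomised arm. If the patient starts a non-study AED in that period, its dizziness, somnolence or ataxia is tabulated as treatment-emergent under lacosamide or placebo. When lacosamide prevents seizures, fewer lacosamide patients reach that point.

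At stake is the toxicity evidence that will stand beside the efficacy result. For AED-type events, the tables that apply no causality filter (all events, worst grade, serious events) would understate the lacosamide excess, and would do so more as lacosamide prevents more seizures.

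**Working it through.** **Inputs.** One-year seizure risk 20% on placebo and 8% on lacosamide, and 15% loss to follow-up (11.1). 151 patients per arm (11.1). Dizziness in more than 20% of patients (3.12). Each event counted once per patient per summary (11.2.5).

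**The plan's own figures.** HR = ln(0.92)/ln(0.80) = 0.3737, which matches "estimate the hazard ratio between the L and P arms to be 0.374". A log-rank simulation (8,000 runs, exponential seizure times, one-year censoring, 15% exponential loss, two-sided 0.05, N = 298) gives 83.6% power, as stated in 11.1. Expected seizures without loss are 151 × (0.20 + 0.08) = 42.3, against the stated 42. The design rates can therefore be used as they stand.

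**Patients entering the window through a seizure.**
- Placebo 151 × 0.20 = 30.2; lacosamide 151 × 0.08 = 12.1; ratio 2.50.
- With 15% exponential loss the risks become 0.185 and 0.074, giving 28.0 and 11.2; ratio 2.50.
- If lacosamide does not reduce seizures, the ratio is 1.0.

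**Upper-end effect on a dizziness table.** Assume that every seizure patient starts an AED, that this AED shows lacosamide's full dizziness rate D = 0.20 within 30 days, and that every event is captured. Let p0 be the placebo background rate, which the documents do not give; it is varied here.
- Added to placebo: 0.20 × (D − p0).
- Added to lacosamide: 0.08 × (1 − D) × (D − p0)/(1 − p0), because patients already counted cannot be added again.

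| p0 | Added, placebo | Added, lacosamide | Net shrinkage | Share of true excess D − p0 |
|---|---|---|---|---|
| 0 | 4.0 points | 1.3 | 2.7 | 13.6% |
| 0.05 | 3.0 | 1.0 | 2.0 | 13.3% |
| 0.10 | 2.0 | 0.7 | 1.3 | 12.9% |

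With the 15% loss the shares are 12.6%, 12.3% and 11.9%. Section 3.12 gives 20% only as the floor of its band. A higher D raises the points, but the share, 0.20 − 0.08 × (1 − D)/(1 − p0), moves little.

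**Milder case (assumed values).** With 70% uptake and half the excess arising within the window, the factor is 0.70 × 0.5 = 0.35. At p0 = 0.05 this gives 2.0 × 0.35 = 0.7 points, or 13.3% × 0.35 = about 5% of the true excess.

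**If seizure risk were 20% in both arms.** Entry to the window is balanced. Once-per-patient counting alone leaves 0.20 × (D − p0)²/(1 − p0), which is 0.8, 0.5 and 0.2 points for the three backgrounds under the same upper-end assumptions.

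**Window time involved.** Mean time on drug, ignoring loss and death, is 365 × 0.20/0.2231 = 327 days on placebo and 365 × 0.08/0.0834 = 350 days on lacosamide. Post-seizure days are 0.20 × 30/(327 + 30) = 1.7% and 0.08 × 30/(350 + 30) = 0.6% of window time.

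**The case against.** The other side has several good points.

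- **Size.** Full uptake, full capture and a whole-trial dizziness rate packed into 30 days are all generous. Even the 1.3 to 2.7 points lie below one standard error of the arm difference at 151 per arm: √(0.16/151) = 3.3 points at p0 = 0, and √((0.16 + 0.09)/151) = 4.1 at p0 = 0.10. Section 11.2.5 names no between-arm test. This stands. It limits the importance of the point but not its direction, since a systematic shift is not removed by being smaller than sampling error.
- **Attribution.** The causality guidance in 15.7 tells investigators to answer no when another drug sufficiently explains the event. The related-event tables are therefore partly protected, although 11.2.5 treats a missing attribution as related. The table of events leading to study drug discontinuation is not affected. This stands.
- **Section 9.3.** The question whether worsening symptoms offset the benefit is assigned to the MDASI-BT. A reader might infer that this question rests on the adverse event tables; the documents do not support that.
- **Capture and permission.** Scheduled adverse event calls are for the time on treatment, and 6.1.2(d) may or may not bar other AEDs after the stop. The number of events affected is therefore unknown. A reader might infer that nothing restricts a new AED, or that it would be lacosamide itself; the documents establish neither. Patchy capture is no safeguard, because whatever is recorded still enters the tables. The explicit follow-up in 15.12 may also fall more on seizure patients, since 15.6 gives a first convulsion as an example of a serious event.
- **Other stops.** Section 2.5 reports discontinuation for adverse events of 17% at 400 mg/day and 5% on placebo in epilepsy trials. If a share s of such patients also started a non-study AED, the ratio of new starts would be (0.20 + 0.05s)/(0.08 + 0.17s): 1.7 at s = 0.25, 1.4 at 0.5 and 1.0 at 1. The documents do not give s.
- **Truncation.** Closing the window at a new AED conditions on an event after randomisation and could hide delayed reactions. Section 2.5 describes hepatitis with nephritis 10 days after lacosamide ended. This is why the 30-day tables should stay and the truncated ones be added.

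**Conclusion.** The point holds as a modest defect in the analysis definition that is cheap to repair. If lacosamide reduces seizures, the unfiltered treatment-emergent tables lean towards no difference for AED-type toxicity, because more placebo patients carry post-seizure days, and possibly a new AED, in their window. At the design rates about 30 placebo and 12 lacosamide patients are in that position. The shrinkage is about 1.3 to 2.7 points (13 to 14% of the true excess) at a 20% dizziness rate with full uptake, full expression within 30 days and full capture. It is about 0.7 points (5%) with 70% uptake and half the excess in the window. If lacosamide does not reduce seizures, the imbalance in entry disappears.

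A reader might infer that side effects of the new AED are counted 2.5 times as often against placebo. The documents do not support that. The 2.5 is the ratio of patients who stop for a seizure. Carrying it over to events would need equal AED uptake, side-effect rates and capture in both arms, and equal on-drug prevalence under once-per-patient counting. None of these is given, and the table above itself yields ratios of 2.8 (2.0/0.71) to 3.1 (4.0/1.28).

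**What to change.** 1. Keep the 30-day treatment-emergent tables in 11.2.5.
2. Add the same summaries by arm with the window ending at the earlier of 30 days after the last dose and the day before the first non-study AED started after study drug ended. Base the between-arm comparison of AED-type toxicity on these. Because the cut-off applies whatever the reason for stopping, it also covers patients who stop for an adverse event.
3. Show events from that AED start to day 30 by arm in a separate table.
4. State that AED start dates and adverse events are recorded through day 30 after the last dose in both arms.
5. Reconcile 6.1.2(d), Figure 8-1 footnote a, 10.1, 11.2.1, 11.2.5 and 15.12 on what applies after a seizure ends study drug. Which clinical rule applies is for the investigators to settle.

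The cost is a few sentences and some extra tables, plus confirmation that concomitant medication and adverse event recording continues to day 30. No extra patients are needed. A delayed study-drug reaction that begins after a new AED would be missing from the truncated table but would still appear in the 30-day and separate tables.
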